3. STUDY DESIGN

Design Overview: A two-group (n = 165/165), randomized, repeated measures design will be employed. Three hundred thirty individuals with OUD engaged in medication treatment will be recruited at one of five outpatient treatment sites: Harborview Medical Center, Country Doctor Community Health Centers, North Olympic Healthcare Network, Cascade Medical Advantage, and Evergreen Treatment Services. Enrolled patients will be individually randomized within sites to receive MABT+TAU (experimental group), or TAU alone (control). Assessments will be administered at baseline, post-intervention (3 months from baseline), and at 6, 9 and 12 months follow-up. An additional six sessions of MABT will be offered to those randomized to MABT who have continued substance use at six months.

Randomization: Following baseline data collection, participants will be randomized to treatment group by the Research Coordinator. [name], the project statistician, provided a randomization program programmed in Microsoft BASIC. Randomization will be specific to each study site and stratified by sex (approximately equal numbers of men and women assigned to each study group at each site) and baseline self-reported chronic pain. The algorithm used for randomization is a modification of a minimization method [96] based on an overall imbalance score which measures how far out of balance (within strata) the study is for a given set of random assignments. Participants will be informed of their assignment within one week of the initial appointment. Prior MABT studies showed no loss due to randomization to treatment group, thus we do not expect randomization to precipitate significant attrition. The Research Coordinator at each facility will not be blind to condition and will inform participants of their treatment condition and MABT therapist.

Measures: The outcome measures are described below (see also Table 1 in Précis).

Primary Objectives: The primary outcome is patient-reported days of illicit opioid use. Self-reported substance use is the recommended approach for intervention studies.[97] Days of illicit opioid use is defined as the number of reported days of use in last 90 days (baseline assessment) or since and including the last assessment date (follow-up assessments) in which opioids other than MAT (buprenorphine or methadone) are reported.

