5. STUDY INTERVENTIONS

5.1 Interventions, Administration, and Duration

The intervention in this study is Mindful Awareness in Body-oriented Therapy (MABT), administered one-on-one by therapists trained in the MABT protocol at the outpatient treatment site where the participant was recruited from and receives their MAT care. Individuals in the MABT intervention group will receive 8 weekly 1.25 hour one-on-one sessions of MABT between baseline and the 3 month follow-up assessment. There are no restrictions to supportive care, medications, or other treatments which intervention group participants may use during their participation in the study with the exception of additional manual (e.g., massage) and/or mind-body therapies of meditation and yoga during the first three months of study engagement (this information is part of the screening process for enrollment, and will be reiterated by the research coordinator at the time of study enrollment). There are no anticipated adverse effects of the intervention other than the possibility of short-term emotional discomfort.

At six months, those in the MABT treatment group with continued substance use will be offered an additional six sessions of MABT between the 6 month and 9 month assessments.

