6.2.4 Follow-up Visits

Treatment

Initial Treatment Visit 1 (W1)

- Adverse Events
- MABT Process Evaluation (self-report by interventionists)

Initial Treatment Visit 2-8 (W2 - 11)

- Adverse Events
- MABT Process Evaluation (self-report by interventionists)
- MABT Practice Log (self-reported home practice by participants for use by interventionists)

Additional MABT Sessions 1-6 (W25 - W38)

- Adverse Events
- MABT Process Evaluation (self-report by interventionists)
- MABT Practice Log (self-reported home practice by participants for use by interventionists)

Assessments

Followup1-4 Assessment Visits (W12, W24, W39)

The follow-up assessments will be scheduled 12 weeks, 24 weeks, and 39 weeks from baseline, and takes approximately 45 minutes to complete. Coordinators will make every effort to schedule the assessment near to the target date, but are allowed -2 weeks/+4 weeks to capture follow-up assessment data. In addition to this assessment, we will also gather treatment retention data through electronic medical record (EMR) at the 6 and 12 month assessments.

Should a participant be unable to provide data during the scheduled assessment (e.g., unable to provide a urine sample, or unable to complete the assessment in one sitting), research coordinators have up to 14 days to complete the data collection for the assessment.

W24: The Time-Line Follow-Back Interview (TLFB)[3, 4] results collected at 6 months will be used to determine those in the MABT study group with continued substance use who will be offered six additional MABT sessions between month 6 and 9. Criteria for eligibility for additional MABT sessions is 1) randomized to the MABT + TAU study group, and b) self-report of substance use on the TLFB, including any days of heavy alcohol drinking and excluding marijuana use.

Primary outcome:

- Time-Line Follow-Back Interview (TLFB)[3, 4] will be used to assess self-reported opioid use, and use of other illicit drugs, marijuana, and alcohol.

Secondary outcomes:

- The PHQ-9 will be used to measure depression symptoms.[6, 7].
- The GAD-7 will be used to measure anxiety symptoms.[8]
- Posttraumatic Stress Disorder Checklist for DSM-5 (PCL-5),[9] assesses symptoms of post-traumatic stress on a Likert-type scale.
- Difficulty in Emotion Regulation Scale - short form (DERS- SF)[10] assesses difficulties in the modulation of emotional arousal.

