7.3 Adverse Events and Serious Adverse Events

For this study, the following standard AE definitions are used:

Adverse event: An adverse event (AE) is any untoward medical occurrence in a subject during participation in the clinical study or with use of the experimental agent being studied. An adverse finding can include a sign, symptom, abnormal assessment (laboratory test value, vital signs, electrocardiogram finding, etc.), or any combination of these

Serious Adverse Event: A serious adverse event (SAE) is any AE that results in one or more of the following outcomes:

- Death
- A life-threatening event
- Inpatient hospitalization or prolongation of existing hospitalization
- A persistent or significant disability/incapacity
- A congenital anomaly or birth defect
- An important medical event based upon appropriate medical judgment

AEs are graded according to the following scale:

Mild: An experience that does not have a major impact on the patient (e.g., is transient, requires no special treatment or intervention, does not generally interfere with usual daily activities). This includes transient laboratory test alterations.

Moderate: An experience that causes the patient some minor inconvenience, but is alleviated with simple therapeutic treatments. The experience impacts usual daily activities. Includes laboratory test alterations indicating injury, but without long-term risk.

Severe: An experience that causes a substantial disruption to the patient's well-being (e.g., requires therapeutic intervention). The experience interrupts usual daily activities. If hospitalization (or prolongation of hospitalization) is required for treatment it becomes an SAE.

The study will use a form specifically for collection of AEs. AEs will be solicited at all participant followup assessment visits with the RC and collected at all intervention visits by the Interventionists. The AE form will have the following attribution scale:

Not related: The AE is clearly not related to the study procedures (i.e., another cause of the event is most plausible and/or a clinically plausible temporal sequence is inconsistent with the onset of the event).

Possibly related: An event that follows a reasonable temporal sequence from the initiation of study procedures, but that could readily have been produced by a number of other factors.

Related: The AE is clearly related to the study procedures.

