7.4 Reporting Procedures

AE Reporting and Follow-up

During the post-intervention and follow-up assessments, the Research Coordinator will inquire about AEs and complete a participant event form (PEF) if an AE is reported. Likewise, MABT Interventionists will complete a PEF form if an AE is reported during check-in's prompted in the intervention protocol. PEF forms will be submitted to the project manager weekly, and all adverse events, with the exception of clinically insignificant events and minor common illnesses and injuries (e.g., cold/flu, scrapes, upset stomach, low-grade headaches) will be documented on an AE Log and will be reported every 2 weeks to the contact PI, who provides the grading and attribution evaluation. AEs will be summarized and discussed monthly amongst the core research team. AE summary reports will be provided quarterly to the independent monitor (IM), and to the NCCIH at the time of the annual progress report. Reports will provide information on cumulative incidents and if in total the events suggest that subjects or others are at greater risk, investigators and the IM will address whether or not the consent form needs to be changed. In the annual AE summary, the Independent Monitor Report will state that he has reviewed all AE reports. If an AE/SAE meets the criteria of unanticipated problem for the UW IRB, it will be reported within 10 business days. Breach in confidentiality will be reported to the IRB within 24 hours.

SAE Reporting

SAEs that are unanticipated, serious, and possibly related to the study intervention will be reported to the IM and NCCIH in accordance with requirements.

- Unexpected fatal or life-threatening AEs related to the intervention will be reported to the NCCIH Program Officer within 7 days. Other serious and unexpected AEs related to the intervention will be reported to the NCCIH Program Official within 15 days.

- Anticipated or unrelated SAEs will be handled in a less urgent manner but will be reported to the IM and NCCIH in accordance with their requirements.

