9.2 Sample Size and Randomization

Sample Size Calculation/Power Analysis:

Primary Objective The power for the primary aim of this study was determined for change in the days percent abstinent from opioids on the Timeline Followback Interview (TLFB) between the study's two arms (MABT +TAU, and TAU only) from baseline to 6 months (R33 aim) and baseline to 12 months (R01 aim). The power analysis was based on the prior MABT SUD R01 study (N=187), in which the proportion of abstinent days for MABT + TAU was 88.6 compared to 80.0 for TAU at 12 month follow-up.[90] Unlike the count data used to assess the number of days abstinent, proportional data is based on exact binomial confidence intervals and thus provides reliable and appropriate data to use for sample size calculation. The magnitude of effect in this prior R01 is expected to be similar for baseline to 6 month (R33) and baseline to 12-month effect for MABT + TAU vs. TAU (R01) in the current study.

A sample of 330, with an expected loss to follow-up of 20%, allows for .80 power to detect a minimum difference in proportion in days abstinent between MABT and TAU of .14, alpha =.05, two-tailed. Loss to follow-up is not expected to vary significantly due to treatment assignment. Since the actual analyses allow GEE models to analyze five time points (0, 3, 6, 9, 12 months) simultaneously for the R01 study, power will very likely be higher than these conservative estimates.

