9.4 Interim Analyses and Stopping Rules

No interim efficacy or futility analyses are planned because of the minimal risk level of the study and because patient outcomes are very unlikely to be worse in the intervention group in the study.

This study will be stopped prior to its completion only after discussion with and input from NCCIH if: (1) the intervention is associated with severe adverse effects that call into question the safety of the intervention; (2) difficulty in study recruitment or retention will significantly

impact the ability to evaluate the study endpoints; (3) any new information becomes available during the trial that necessitates stopping the trial; or (4) other situations occur that might warrant stopping the trial.

Pertaining to the likelihood of adverse events, prior studies employing MABT to individuals with mental health concerns including two NIH-funded studies for individuals with substance use disorder, many of whom had moderate-severe depression and/or anxiety symptoms, and three additional studies for women with sexual trauma, have not identified significant risks associated with this intervention. However, should adverse events occur that are determined to be related to study participation, the MPIs and independent monitor (IM) will consult with both the UW IRB and the NICCH Program Officer about the likelihood of continued risk to study participants and will make a decision about whether it is necessary to stop the trial.

Should accrual monitoring demonstrate the need, the MPIs will consult with the data analyst and the IM to assess the impact of significant data loss due to problems in recruitment, retention, or data collection. Factors external to the study when interpreting the data, such as scientific developments or the new availability of proven clinical services that could have an impact on the safety of the participants, the performance of the study or the ethics of the study, will be reviewed by the MPIs annually.

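### Scheduled adverse event collection is up to 12–18 occasions in MABT against 4 in TAU, and no procedure is described for finding serious events in participants who miss assessments

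*Combined protocol and SAP*

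**What the plan says.** Section 7.3 sets two routes: "AEs will be solicited at all participant followup assessment visits with the RC and collected at all intervention visits by the Interventionists". Section 7.4 has the coordinator inquire at each follow-up assessment and adds that "MABT Interventionists will complete a PEF form if an AE is reported during check-in's prompted in the intervention protocol". Forms from both routes go to the project manager. Events other than clinically insignificant ones and minor common illnesses or injuries are then entered on a single AE Log, and the contact PI grades and attributes them.

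The assessments are common to both arms (Section 3): "Assessments will be administered at baseline, post-intervention (3 months from baseline), and at 6, 9 and 12 months follow-up". The sessions are not. Section 5.1 states: "Individuals in the MABT intervention group will receive 8 weekly 1.25 hour one-on-one sessions of MABT between baseline and the 3 month follow-up assessment". MABT participants with continued substance use at six months "will be offered an additional six sessions of MABT between the 6 month and 9 month assessments". The adverse event row of the schedule in Section 6.1 marks all the treatment visits, all the booster visits and the W12, W24, W39 and W52 assessments. It does not mark baseline.

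On use of safety data, Section 9.4 lists as its first ground for stopping that "the intervention is associated with severe adverse effects that call into question the safety of the intervention". Section 7.6 makes the annual safety tables aggregate, and Section 9.6 contains no adverse event analysis. The power calculation in Section 9.2 is made "with an expected loss to follow-up of 20" per cent. On records, Section 6.2.4 says "we will also gather treatment retention data through electronic medical record (EMR) at the 6 and 12 month assessments". The stated use of the record is retention and the date of program discharge.

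**The concern.** A TAU participant is asked about adverse events after gaps of 12 to 15 weeks. A MABT participant is seen about weekly for much of the first 12 weeks, and again between months 6 and 9 if given the additional sessions. An event of moderate severity that resolves in days is more likely to be recorded in MABT even when the true rates are equal. Nothing in the plan requires the two routes to be kept apart on the log, so a comparison drawn from it would mix a difference in safety with a difference in the number of contacts.

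There is a second gap, in both arms. Scheduled collection depends on attendance. Death and inpatient hospitalisation are serious adverse events under Section 7.3, yet no step is described for finding them in someone who stops attending.

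The stake is the trial's ability to answer its own safety question. An apparent excess in MABT could come from more frequent contact, and serious events among absent participants could go unrecorded.

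**Working it through.** The plan gives no number of adverse event contacts per arm and no expected event rate, so there is no figure of its own to reproduce.

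**Inputs from the plan.** Follow-up assessments: 4 (Section 3; schedule in 6.1). Initial sessions: 8. Additional sessions: up to 6, scheduled in W25–38 (Sections 5.1 and 6.1). Sample size 330 and loss 20% (Section 9.2). Non-responder rate at 6 months: 40% (Section 9.2, a power assumption). Assessment window: −2 to +4 weeks (Section 6.2.4).

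**Step 1: scheduled occasions.**
- TAU: 4.
- MABT: 4 + 8 = 12, which is 3.0 times TAU. With additional sessions, 12 + 6 = 18, which is 4.5 times TAU.
- First 12 weeks: 8 sessions + W12 = 9 in MABT, 1 in TAU.
- Mean in MABT with full attendance and 40% receiving the additional sessions: 12 + 0.4 × 6 = 14.4.
- These are maxima. A MABT participant who attends no sessions but every assessment has 4; one who attends six of the eight initial sessions and no additional ones has 4 + 6 = 10.

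**Step 2: recall interval in TAU.** W12 to W24 is 12 weeks and W24 to W39 is 15. With W24 done two weeks early and W39 four weeks late, the gap is 15 + 2 + 4 = 21 weeks.

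**Step 3: spurious ratio while sessions run.** Assumption, not in the plan: a transient event is reported with probability 0.9 if asked about within about a week, and with probability q between 0.3 and 0.8 if asked about at the next assessment. With equal true rates, the MABT:TAU ratio is 0.9/q, so 0.9/0.8 = 1.1 and 0.9/0.3 = 3.0.

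**Step 4: dilution over the year.** Outside the session periods the schedules are identical. With c weeks covered by sessions and events spread evenly over 52 weeks:

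ratio = [0.9c + q(52 − c)] / (52q)

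| | q = 0.8 | q = 0.3 |
|---|---|---|
| Initial sessions, c = 12 | (10.8 + 32.0)/41.6 = 1.03 | (10.8 + 12.0)/15.6 = 1.46 |
| Plus W25–38, c = 12 + 14 = 26 | (23.4 + 20.8)/41.6 = 1.06 | (23.4 + 7.8)/15.6 = 2.0 |

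**Step 5: a second recall model.** As a check, let recall at the next contact be exp(−lag/τ), with events uniform over 52 weeks, weekly sessions in weeks 1–8 and additional sessions every two weeks in weeks 26–36. All of these are assumptions.

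| τ (weeks) | First 12 weeks | Year, 12 contacts | Year, 18 contacts |
|---|---|---|---|
| 4 | 2.53 | 1.38 | 1.88 |
| 12 | 1.46 | 1.11 | 1.27 |
| 52 | 1.10 | 1.02 | 1.06 |

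The two models agree in direction and rough size. The distortion is large early on for quickly forgotten events and slight for events that are remembered for months.

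**Step 6: participants lost.** 330 × 0.20 = 66, or 33 per arm if loss is equal.

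**The case against.** Several parts of the opposing case stand.

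- **Asking is not the only route.** A reader might infer that events come to light only when someone asks. Section 7.1 requires same-day reporting of emergencies, suicidal ideation and other urgent concerns met by study staff, and a signed release allows two-way communication with clinic staff. Section 7.5 has events managed jointly with them. None of this is scheduled surveillance, however, and interventionists see only one arm.
- **A session is not necessarily an adverse event question.** Section 7.3 uses different verbs for the coordinator and the interventionist, and Section 7.4 relies on prompted check-ins. The counts are opportunities to report.
- **No planned analysis is affected.** Section 7.6 pools the annual tables, Section 9.6 compares nothing by arm, and attribution is made event by event. Nothing says that the first stopping criterion rests on a comparison of rates.
- **The log leaves out trivial events, and severe ones are remembered.** Both facts shrink the bias where it would be largest or would matter most. The short-term emotional discomfort and anxiety that Sections 5.1 and 7.1 anticipate are not among the examples left off the log.
- **Data collected equally in both arms exist.** Health-utilisation questions and the symptom scales are given to both arms at every assessment. They help for those who attend, but not for those who do not.
- **Frequent monitoring of a touch-based therapy is reasonable, and the bias runs against MABT.** That is a reason to keep session reporting. It does not justify mixing it into a comparison.

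It is also tempting to say that those lost are those who relapsed. Section 2.1 ties relapse to leaving care, whereas the 20% is loss from the study, and Sections 5.3.1 and 5.3.2 keep following people who stop medication treatment. The documents do not show that those lost are at highest risk.

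**Conclusion.** The point holds in a limited form. Scheduled collection differs by arm, at up to 12–18 occasions against 4, and feeds one log. Any comparison by arm drawn from that log would be biased towards an excess in MABT, mainly for non-trivial but quickly forgotten events. The ratios in the working depend on assumed recall. The figure of 3.0 is the extreme for the period while sessions run and should not be read as an effect over the year.

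Two stronger readings are not supported. The plan does not commit to a biased comparison, because it specifies none; it simply has no safeguard if one is made. Nor does it say that events after loss to follow-up will never be learned of. It is silent on any procedure for finding them beyond unscheduled staff reports and contact with clinic staff. That silence, for about 66 expected participants, is the more consequential half where deaths and hospitalisations are concerned.

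**What to change.** 1. **Identify the source of each event** on the participant event form: coordinator assessment or MABT session. State that any comparison by arm will use only events elicited by the coordinator at W12, W24, W39 and W52, with the same questions about the whole interval in both arms, whether or not an event was already mentioned in a session. List session-reported events separately. The cost is one field and a table footnote, or less if the form already shows who completed it (the form is not in the documents). The coordinator is not blind to arm (Section 6.2.3), so this equalises how often people are asked but not every source of reporting bias.

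2. **Extend the 6- and 12-month record extraction.** For every randomised participant, including those who have missed assessments, also record death, hospitalisation, overdose and reason for program discharge, and log qualifying events as serious adverse events. This adds a few items to a chart already being opened. An IRB modification may be needed, since Section 6.2.2 describes the release as covering limited data elements. Clinic records will miss events treated elsewhere or occurring after program discharge, so the gap would be narrowed and not closed.
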